**Registration number : NCT06435624**

**Proposed date : June 15, 2024**

Study Start	June 15, 2024		
Primary Completion	August 31, 2024		
Study Completion	August 31, 2024		
Objective	To investigate the effectiveness of Intelligent robotic-assisted training (IRAT) combined with Repetitive facilitative exercise (RFE) on upper limb motor function in stroke patients		
Design	Randomized controlled trial		
Ethical Board	Medical Ethics Management Committee of Nanjing Mingzhou Rehabilitation Hospital		
Approval Number	NJKF202401001		
Location	Nanjing Mingzhou Rehabilitation Hospital, [name]		
Randomization	Closed envelope method		
Masking	Single blind design (Outcomes assessor)		
Arms	IRAT group	RFE group	CT group
Enrollment	30	30	30
Interventions	IRAT (30min) + RFE (30min)	RFE (60min)	CT (60min)
Outcome Measures	Fugl-Meyer assessment for upper extremity Active participation proportion Trajectory deviation Trajectory tracking error		
Inclusion Criteria	Patients (18 to 74 years old) who suffered a first or Second unilateral stroke; Chronic stroke (over 6 months from the onset); Obvious upper limb movement disorders (FMA-UE scores from 25 to 42); Ability to understand and follow simple directions		
Exclusion Criteria	Pregnant or lactating; Upper extremity contracture, pain, or trauma; Perceptual, apraxic, or cognitive deficits that lead to inability to follow verbal instructions; Unable to maintain sitting posture; Cerebellar lesion; Clinically unstable medical disorders; Inability to provide informed consent		

Statistical analysis	
Sample size calculation: G*power 3.1.9.7 software was used to calculate the sample size. Using the FMA-UE scores from a pilot study, we calculated the effect size <math>f</math> to be 0.374. With an alpha level of 0.05 and a power of 0.80, the total sample size was calculated to be 72.
 
Statistical analysis method: SPSS 21.0 software was used to calculate the demographic and outcome measures. The Shapiro-Wilk test was used to assess the distribution of quantitative variables. Since all variables followed a normal distribution, a one-way analysis of variance was performed to compare the three groups. For post-hoc test, Bonferroni correction was applied when equal variances were assumed, and Tamhane's T2 was used when equal variances were not assumed. A paired samples t - test was used to compare data before and after the intervention. The chi-square test was used to compare qualitative variable. All significance tests were two-tailed, with p values <math><0.05</math> considered statistically significant.

----------------------	--

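### The between-arm FMA-UE analysis ignores baseline and does not say whether post-treatment or change scores are used; the ANOVA is valid, but ANCOVA would be a nearly free improvement

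*Combined protocol and SAP*

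**What the plan says.** The Statistical analysis section of the combined protocol and SAP states that "a one-way analysis of variance was performed to compare the three groups". The pairwise follow-up depends on the variances: "For post-hoc test, Bonferroni correction was applied when equal variances were assumed", and "Tamhane's T2 was used when equal variances were not assumed". A chi-square test is kept for qualitative variables. No covariate, mixed model or group-by-time term is named.

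On the score itself, the Outcome Measures row reads "Fugl-Meyer assessment for upper extremity Active participation proportion Trajectory deviation Trajectory tracking error", with no time point and no indication of post-treatment value or change. The sample size paragraph is equally open: "Using the FMA-UE scores from a pilot study, we calculated the effect size".

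Baseline values exist. Entry requires "Obvious upper limb movement disorders (FMA-UE scores from 25 to 42"), and the plan also says "A paired samples t - test was used to compare data before and after the intervention", which needs a pre-treatment measurement.

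**The concern.** The paired t-test works within an arm and estimates no difference between arms. The treatment comparison therefore rests on the ANOVA and its pairwise follow-up, and neither is adjusted for baseline.

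- **If post-treatment scores are analysed**, baseline is ignored. The variance it explains stays in the error term, and a chance baseline difference between arms carries over into the estimated effect.
- **If change scores are analysed**, baseline enters with its slope fixed at 1. That is the best slope only when the ratio of baseline SD to post-treatment SD equals the baseline–post correlation.

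The two analyses can give different answers from the same data. Leaving the score unstated allows the choice to be made after results are seen. ANCOVA removes this dependence: with baseline in the model, the arm differences are identical whether the outcome is entered as post-treatment value or as change.

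Precision matters most for the pairwise contrasts, because the objective concerns one particular combination of treatments and an omnibus test alone does not answer it.

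**Working it through.** **Inputs from the documents.** Three arms of 30 (total 90); f = 0.374; two-sided alpha 0.05; target power 0.80; calculated total 72.

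**Assumptions, not in the documents.** ρ is the correlation of baseline with post-treatment FMA-UE, taken as 0.3 to 0.9. s is baseline SD divided by post-treatment SD, taken as 0.7, 0.8 and 1.0; a value below 1 is plausible because entry is limited to 25–42.

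**1. The plan's own figure.** One-way ANOVA, noncentral F with λ = f²N and df (2, N−3).
- N = 69: power 0.781.
- N = 72: λ = 0.374² × 72 = 10.07, power 0.800. The stated 72 reproduces, for an unadjusted ANOVA.
- N = 90: λ = 12.59, power 0.887.

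**2. Residual variance.** Set the post-treatment SD to 1.
- Post-score ANOVA: 1.
- Change-score ANOVA: 1 + s² − 2ρs = (1 − ρ²) + (s − ρ)².
- ANCOVA: 1 − ρ².

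The ANCOVA variance is never the largest of the three. It equals the change-score variance only at ρ = s.

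**3. Omnibus power with ANCOVA**, df (2, N−4).

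If f refers to post-treatment scores, λ = f²N/(1 − ρ²). For ρ = 0.3, 0.5, 0.7:
- N = 90: 0.916, 0.959, 0.995.
- N = 72: 0.838, 0.904, 0.980.

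If f refers to change scores, λ = f²N(1 + s² − 2ρs)/(1 − ρ²). At N = 90:

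| s | ρ = 0.3 | 0.5 | 0.7 | 0.8 | 0.9 |
|---|---|---|---|---|---|
| 1.0 | 0.979 | 0.959 | 0.933 | 0.919 | 0.903 |
| 0.8 | 0.951 | 0.921 | 0.894 | 0.887 | 0.903 |

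With s = 0.7 the range is 0.887 (at ρ = 0.7) to 0.940 (at ρ = 0.9). At N = 72 with s = 0.8 the values are 0.891, 0.845, 0.808, 0.800 and 0.821.

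**4. Pairwise power at N = 90.** Noncentral t, alpha 0.05/3, 30 per arm, df 87 unadjusted and 86 adjusted. The pattern of arm means is not given, so two are shown.
- One arm differs from the other two: d = f × 3/√2 = 0.793. Power 0.735 becomes 0.780 to 0.967 (post, ρ 0.3–0.7) or 0.735 to 0.912 (change, all s and ρ above).
- Equally spaced arms, adjacent pair: d = f × √6/2 = 0.458. Power 0.258 becomes 0.286 to about 0.52 (post) or 0.258 to 0.409 (change).

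**5. Chance imbalance.** The standard error of a baseline difference between two arms is √(2/30) = 0.258 baseline SD. If baseline were uniform over 25–42 (an assumption; SD 4.9 to 5.2), that is about 1.3 FMA-UE points. A one-SE imbalance shifts the estimated arm difference as follows.
- Post scores: ρ × 0.258, or 0.08 to 0.23 post SD for ρ = 0.3 to 0.9.
- Change scores: (ρ − s) × 0.258. At s = 0.8 this is −0.13, −0.08, −0.03, 0 and +0.03 for ρ = 0.3, 0.5, 0.7, 0.8 and 0.9. At s = 1.0 it is −0.18 to −0.03.

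**6. Cost and validity.** By formula, a useless covariate (ρ = 0, post scores) leaves power at 0.887. The formula counts the lost degree of freedom but not the cost of estimating the slope, so simulation was used as well (20,000 runs per setting, f on change scores, N = 90), comparing change-score ANOVA with ANCOVA.
- s = 0.8, ρ = 0.5: 0.886 against 0.918.
- s = ρ = 0.8: 0.885 against 0.882.
- s = ρ = 0.7: 0.886 against 0.882.
- s = ρ = 0.8 with a uniform integer baseline over 25–42: 0.890 against 0.885.

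Type I error was 0.047–0.055 for ANOVA and 0.046–0.054 for ANCOVA, so both are valid.

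**The case against.** A one-way ANOVA is a legitimate analysis of a randomised trial, and the sample size was calculated for that same test, so plan and calculation agree. Enrolment of 90 is 18 above the calculated 72, which already gives omnibus power of 0.887 against a target of 0.80. The size of the gain is unknown. For change scores with s = 0.8 and ρ between 0.7 and 0.9 it is at most 1.6 points (0.903 against 0.887), and the entry window may lower ρ, which reduces the gain over post scores. Chance imbalance does not bias the ANOVA; the shifts in step 5 are the same baseline-related variance already counted in the power figures, not a second harm. Finally, the section is written in the past tense, so ANCOVA may come too late to be a prespecified analysis.

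All of this is right, and it limits the point to efficiency and clarity. It does not remove it. The omnibus margin does not extend to every pairwise contrast: with equally spaced arms, power for an adjacent pair is 0.258 at N = 90. The cost is a fraction of a percentage point at worst. And none of these arguments supplies the missing definition of the score.

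**Conclusion.** The point holds, as an improvement that should be made and not as an error. The plan names no baseline adjustment for any between-arm comparison and leaves the analysed FMA-UE score undefined. The stated test is valid, and 72 is correct for it.

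At N = 90 the omnibus gain from ANCOVA is about 0 to 11 percentage points over 0.887. It is nil for change scores when ρ = s, where simulation puts ANCOVA 0.3 to 0.5 of a point lower. The possible pairwise gains are larger: up to 0.967 from 0.735, and to about 0.52 from 0.258. The absence of a covariate and of a defined score is certain from the text. The size of the benefit rests on assumed values of ρ and s, on assumed patterns of arm means, and on which score the pilot effect size describes.

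**What to change.** 1. State whether the FMA-UE analysis, and the pilot f of 0.374, refer to post-treatment or change scores, and give the time point.
2. Make the main between-arm FMA-UE analysis an ANCOVA: post-treatment FMA-UE as outcome, arm as factor, baseline FMA-UE as covariate. Report the three adjusted pairwise differences with 95% confidence intervals and Bonferroni-adjusted tests.
3. If variances are unequal, use heteroscedasticity-robust standard errors in the same model, since Tamhane's T2 compares unadjusted means. In a simulation with arm residual SDs of 1:1:2 and ρ = 0.5 (20,000 runs), per-contrast error against a nominal 0.0167 was 0.001–0.034 with ordinary standard errors and 0.014–0.019 with HC3; familywise error with HC3 was 0.042.
4. Treat any other outcome that has a pre-treatment value in the same way.
5. Keep the one-way ANOVA as a sensitivity analysis, with its score stated.
6. If outcome data have already been seen, report the ANCOVA as a post hoc addition.

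The cost is a change of wording and one error degree of freedom (N−4 instead of N−3). No new data are needed.

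### The before-after paired t-test is uncontrolled and has no stated role; effectiveness should rest explicitly on a baseline-adjusted comparison between arms

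*Combined protocol and SAP*

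**What the plan says.** The synopsis table describes a randomised controlled trial with 30 patients in each of three arms. The objective is the effectiveness of robotic-assisted training combined with RFE. The Interventions row gives every arm 60 minutes of therapy: 30 minutes IRAT plus 30 minutes RFE, 60 minutes RFE, or 60 minutes CT.

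Under Statistical analysis, the between-arm test is "a one-way analysis of variance was performed to compare the three groups". The follow-up comparisons are adjusted: "For post-hoc test, Bonferroni correction was applied when equal variances were assumed", with Tamhane's T2 otherwise. The variable entering the ANOVA is not named.

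A later sentence in the same paragraph adds: "A paired samples t - test was used to compare data before and after the intervention". It does not say which arm or arms are tested, and it does not call the test primary, secondary or descriptive. The paragraph closes with a rule that covers the paired test too: "All significance tests were two-tailed", at p<0.05. No sentence says which test decides effectiveness.

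On sample size, with an effect size f of 0.374 from pilot FMA-UE scores, the plan states: "With an alpha level of 0.05 and a power of 0.80, the total sample size was calculated to be 72".

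**The concern.** The objective concerns the effect of one regimen relative to the others, and only a contrast between randomised arms measures that. A paired test within the IRAT arm asks whether those patients changed at all. It responds to anything the arms have in common, such as an hour of active therapy or familiarity with the assessments on a second occasion. In this design some change in every arm is plausible whether or not the robot adds anything.

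Two misreadings are then available. A significant before-after result in the IRAT arm can be presented as evidence that the combination works. A significant result in IRAT beside a non-significant one in CT can be presented as a difference between them, although no difference has been tested. The plan rules out neither. Because it also leaves the ANOVA variable open, the paired test is the only test that the text explicitly ties to before-after change.

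**Working it through.** **1. The plan's own figure.** Inputs from the sample size paragraph: f = 0.374, alpha 0.05, power 0.80, three groups. For the one-way ANOVA omnibus test, power comes from a noncentral F with df = (2, N − 3) and noncentrality λ = N·f².
- N = 71: λ = 71 × 0.374² = 9.93, power 0.794.
- N = 72: λ = 72 × 0.374² = 10.07, power 0.800.

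The stated 72 reproduces exactly, so the trial is sized on the between-arm comparison and not on the paired test.

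**2. The paired test when all arms change equally.** Inputs: n = 30 per arm (Enrollment row) and two-sided alpha 0.05. Assumptions: the same true mean change in every arm, equal to d SDs of the change score; normally distributed changes; independent arms. The documents give neither a mean change nor an SD of change, so d is varied.

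The critical value is t(0.975, 29) = 2.045. The smallest observed mean change that reaches significance is 2.045/√30 = 0.373 SD. The probability p of a significant improvement in one arm is the upper tail beyond 2.045 of a noncentral t with 29 df and noncentrality d√30. With arms independent, IRAT significant and CT not has probability p(1 − p).

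| d | d√30 | p (IRAT significant) | p(1 − p) (IRAT significant, CT not) |
|---|---|---|---|
| 0.2 | 1.095 | 0.184 | 0.184 × 0.816 = 0.150 |
| 0.3 | 1.643 | 0.355 | 0.355 × 0.645 = 0.229 |
| 0.5 | 2.739 | 0.754 | 0.754 × 0.246 = 0.185 (0.1855 before rounding) |
| 0.8 | 4.382 | 0.988 | 0.988 × 0.012 = 0.012 (0.0114 before rounding) |

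**3. The between-arm test in the same scenario.** A one-way ANOVA on change, simulated 40,000 times at each value with 30 per arm, rejected in 0.049, 0.051 and 0.049 of trials at d = 0.3, 0.5 and 0.8. The shared change cancels in the comparison, so the error rate does not depend on d.

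**4. Cost of adjusting for baseline.** ANCOVA with one covariate has df = (2, N − 4). Holding f at 0.374, N = 72 gives power just under 0.800, and the smallest N that reaches 0.80 is 73. With all 90 enrolled patients analysed, λ = 90 × 0.374² = 12.59 and power is 0.887. This counts only the lost degree of freedom and takes no credit for any variance that the baseline score explains.

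**The case against.** The strongest reply is that the controlled analysis is already there. The ANOVA with adjusted post-hoc tests precedes the paired test in the same paragraph, and the sample size is built on it. In the equal-change scenario, a randomised comparison of either post scores or change rejects about 5% of the time under the usual ANOVA assumptions. This stands. A reader might infer that change is examined only inside each arm, or that the trial lacks a controlled test of its objective. The text does not support either reading: the ANOVA variable is unnamed, and change is not excluded.

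A second reply is that a shared threshold is not a shared role. The p<0.05 rule covers the chi-square test as well, and nothing says that a paired p-value will support a claim of effectiveness. This also stands. The plan does not give the paired test equal standing with the ANOVA; it gives it no standing at all, and that silence is the gap.

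Third, testing each arm separately is an inference. It is the natural one in a three-arm trial, and pooling the arms would be just as uncontrolled.

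Fourth, the probabilities depend on d. They are power to detect a real within-arm change, and become false positives only when read as treatment effects. The discordant pattern falls to 0.01 at d = 0.8, although by then the IRAT arm is significant 99% of the time.

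Finally, it is tempting to cite regression to the mean because patients are selected on "Obvious upper limb movement disorders (FMA-UE scores from 25 to 42" points. That window is bounded on both sides, and the documents give neither the source population's mean nor the retest reliability. Direction and size are unknown, and the point does not rely on it.

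**Conclusion.** The point holds as a defect of role and specification. The planned ANOVA is valid and the sample size is unaffected. What remains is an uncontrolled significance test with no declared purpose, beside a controlled test whose outcome variable is not declared. Under equal true change in all arms, the paired test is significant in the IRAT arm in 18% to 99% of trials over d = 0.2 to 0.8, and the IRAT-yes, CT-no pattern reaches 23% at d = 0.3, against about 5% for the between-arm test. These figures rest on 30 analysed patients per arm, normal and independent changes, and assumed values of d. They measure how easily the paired results could mislead. They do not show that the plan intends to use them in that way.

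**What to change.** - Report each arm's mean change and SD descriptively, without using a p-value as evidence of effect.
- Name the analysis that decides effectiveness: ANCOVA of the post-intervention score with the baseline score as covariate. Give multiplicity-adjusted contrasts and confidence intervals for IRAT+RFE versus RFE and for IRAT+RFE versus CT. This also settles which variable the between-arm analysis uses.
- Add one sentence stating that no claim of effectiveness will rest on significance within an arm or on comparing significance between arms.

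The cost is a change of wording in the analysis plan. The before and after measurements are already planned, and the 90 patients to be enrolled exceed the 73 that ANCOVA needs at the stated f. The downside is that pre-post p-values are no longer reported as results.
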